## 1. STUDY OBJECTIVES

Hypothesis: Surface Electrical Stimulation (SES) contracts pelvic floor muscles. It is not clear which muscles and how much contraction is produced.

### 1.1 Primary Objective

The primary objective is to assess pelvic floor muscle contraction with SES

**Key Endpoints:** *Displacement of bladder base during contraction.*

### 1.2 Secondary Objectives

The secondary objective is to understand which muscles are moving.

## 2. BACKGROUND AND RATIONALE

### 2.1 Background on Condition, Disease, or Other Primary Study Focus

Urinary incontinence (UI) is a widely prevalent condition affecting approximately 1 in 3 women over the age of 30, and 1 in 2 women over the age of 50, and is a major problem after prostatectomy. Although a very private concern, it has far-reaching physical, psychological, social, and economic implications. For example: UI has been found to reduce health-related quality of life measures, with a strong correlation with depression, UI is the number one reason for entry into nursing homes, and the annual cost to Medicare has been estimated at \$10 billion, and at \$20 billion for the entirety of the US healthcare system. 75% of these women are specifically affected with Stress Urinary Incontinence (SUI), which is the loss of continence due to weakened pelvic floor muscles, resulting from a variety of factors including child-bearing, athletic pursuits, trauma, and aging. Their urine leakage occurs when physical exertion (e.g. sneezing, lifting, running) increases intra-abdominal pressure. There are no medications that

address SUI, and while surgery can provide relief, it is painful, expensive, and requires hospitalization and multiple weeks of recovery.

Non-surgical strengthening of the pelvic floor muscles has proven effective in treating most SUI, and this is typically achieved through Kegel exercises, biofeedback, weighted cones or intravaginal electrical muscle stimulation (EMS). However, subjects routinely struggle to perform Kegel exercises correctly or with sufficient frequency (3x/day for 3-6 months) which leads to low compliance. Introducing intravaginal devices or an intravaginal probe necessitates a private location and dedicated treatment time (often at a treatment center), further challenging the likelihood of adoption.

To complicate matters, 4 out of 5 sufferers do not speak with their primary care physician until symptoms have intensified and persisted for numerous years (6.5 years on average), and others fail to consult a specialist (i.e. urologist) because they have no intent of having surgery. This leads to two thirds of affected women suffering quietly without treatment while conditions worsen. Thus, the need exists for a non-surgical means of strengthening the pelvic floor muscles that has a higher rate of subject adoption and compliance than current solutions.

## **2.2 Study Rationale**

Use of intravaginal EMS for treatment of SUI is predicated on the assumption that proximity of the electrodes to the pelvic floor muscles is of primary importance. This is largely accurate. However, appreciating that subjects who seek help most often ultimately fail treatment due to adoption and compliance issues, it is equally important to consider whether the psychological or physiological barriers associated with intravaginal EMS offset any benefit from the treatment's intimate electrode placement.

Several recent clinical reports suggest that a pattern of surface electrodes placed in the suprapubic and ischial tuberosity regions are as effective as intravaginal electrodes at retraining the pelvic floor muscles. In these studies, treatment was administered by a clinician who placed four separate electrodes on the defined tissue region and delivered prescribed pulse waves during regular training sessions. Unfortunately, the need to deliver this treatment in a clinical environment makes it burdensome to the subject and the health system.

Building on these findings, Elidah has developed a wearable, SUI specific EMS device configured for application by the subject and for use outside the clinic, allowing treatment at home and potentially accelerating the rate and efficacy of muscle retraining. This surface EMS device (SES) has been used clinically, with subject's confirmation of pelvic floor contractions. However, a more objective proof that the pelvic floor is actually contracting was requested, and subsequently an identification of which pelvic floor muscles would allow insight into the mechanism of SES.

## **3. SELECTION AND ENROLLMENT OF PARTICIPANTS**

### **3.1 Inclusion Criteria**

All subjects must meet all the inclusion criteria to participate in this study. Any waiver of these inclusion and exclusion criteria must be approved by the Investigator on a case-by-case basis prior to enrolling the subject, and must be documented by the Investigator and the Sponsor.

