### **3.2 Exclusion Criteria**

A subject meeting any of the exclusion criteria at baseline will be excluded if:

- Moderate-severe stress incontinence\*: As determined by self-reported >3 accidents in 24-hr period
- Currently pregnant, may be pregnant (Unsure pre and peri-menopausal women should take a pregnancy test.)
- Active urinary tract infection (UTI)
- Pelvic pain, Painful bladder syndrome, underlying neurologic/neuromuscular disorder that may impact ability to partake in the trial
- implanted cardiac device or untreated cardiac arrhythmia
- Obesity as defined by BMI  $\geq 30$  (height, weight recorded)
- Anyone with impaired decision making, drug or alcohol dependence, or potentially suicidal.
- Anyone who lacks the capacity to consent for themselves or who requires a legal representative to give informed consent

\* Stress urinary incontinence: as determined by an answer of "Yes" to a standard question (from King's Health Questionnaire): "Do you lose urine with physical activities such as coughing, sneezing, running?"

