### **9.3 Data and Safety Monitoring Plan**

The Clinical director of Sponsor will oversee safety data collection as reported from subjects. Demonstration of use will be at the first visit, Instructions for Use will be sent home with the subjects, and a phone number for both the site and study sponsor will be provided to the subjects for any questions or reporting of adverse events. After the first week of use at home, a call will be made to each subject to ensure the subjects are using the device correctly and do not have any issues. Currently, electrical stimulation, such as TENS units, are sold over the counter and are used at home,

so we believe this level of monitoring is considered appropriate and the overall likelihood of harm is low.

To ensure that the rights and well-being of human subjects are protected; the reported trial data are accurate and complete, and verifiable from source documents; and the conduct of the trial is in compliance with the currently approved protocol, with GCP, and with the applicable regulatory requirements, an experienced Clinical Director will monitor the conduct of the study halfway through enrollment of both Phases of the study. In the plan, the clinical director will throughout the trial period:

- Act as the main line of communication between the Sponsor and the investigator
- Verify that facility, laboratories, equipment and staff are adequate to safely and properly conduct the trial
- Verify that the investigator
  - is adequately informed about the trial, as well as investigators' staff
  - has adequate qualifications and resources
  - follows the approved protocol and any amendments
  - receives all documents and supplies necessary
  - is enrolling only eligible subjects
  - provides all the required reports, notifications, applications and submissions
- Verify, for the investigational product:
  - That the storage times and conditions are acceptable, and that supplies are sufficient throughout the trial
  - That the SU1 product is supplied only to subjects who are eligible to receive it and with the correct quantity
  - That the subjects are provided with necessary instruction on proper use, handling, storage, and return of the product
  - That the receipt, use, and return of the product are controlled, documented, and complies with regulations
- Verify that written informed consent was obtained before each subject's participation in the trial
- Report subject recruitment rate

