### **10.2 Informed Consent Forms**

An informed consent document that includes both information about the study and the consent form will be prepared and given to the subject. The document will be prepared in a language understandable to the subject and appropriately describes the responsibilities of the study staff and subject in partaking in the study and any potential risks. An individual from the Study site will review every page with the study subject. The subject is free to ask any questions and may take as much time to read through the document as possible.

If the subject agrees to the informed consent, they will sign two copies of the informed consent and the staff who gave informed consent will also sign both copies. One signed copy will remain in the subject folder, the second copy will be given to the study subject.

No minors will be enrolled in the trial, and those that are unable to consent for themselves will not be eligible to participate by a legal guardian. Individuals who do not speak English will be excluded from enrolling in this study in addition to those who cannot read. Due to the independent and at-home nature of the trial these populations would not be able to perform the daily activities required and no extra provisions will be made for them.

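### Section 3.1 allows any inclusion or exclusion criterion to be waived, with none exempt, so the pregnancy, cardiac and capacity-to-consent exclusions can be set aside as written, in conflict with sections 4.2 and 10.2

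*Combined protocol and SAP*

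**What the plan says.** Section 3.1 opens with an absolute rule: "All subjects must meet all the inclusion criteria to participate in this study". The next sentence reads "Any waiver of these inclusion and exclusion criteria must be approved by the Investigator on a case-by-case basis", and continues "prior to enrolling the subject, and must be documented by the Investigator and the Sponsor". A waiver is thus prospective, individual and documented by two parties, but only the Investigator approves it.

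The exclusions in 3.2 include "Currently pregnant, may be pregnant", "implanted cardiac device or untreated cardiac arrhythmia" and "Anyone who lacks the capacity to consent for themselves or who requires a legal representative to give informed consent". Nothing in 3.1 or 3.2 marks any of them as outside the waiver.

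Other sections also bear on who may enter:

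- **4.2** makes explaining and obtaining consent conditional on the subject meeting the criteria.
- **9.3** has the clinical director verify that the investigator "is enrolling only eligible subjects" and that the product reaches only eligible subjects.
- **10.2** states that "those that are unable to consent for themselves will not be eligible to participate by a legal guardian".
- **9.4.4** requires deviations to be reported to the sponsor within 48 hours and logged.
- **10.1** requires IRB approval of the protocol and of later modifications.

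**The concern.** Eligibility criteria in a device study do two jobs: they keep out people for whom the procedure is judged unsuitable, and they define the group that the results describe. A waiver clause with no exempt criteria weakens both, and the first matters more here. Under 3.1 a woman with an implanted cardiac device, or who is pregnant, could be stimulated with the study still compliant with its own protocol, provided that the Investigator approved beforehand and the paperwork was complete. The protocol chose to exclude these women and then left that choice open to individual discretion.

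The second issue is that the sections cannot all be followed at once. Staff working from 4.2 or 10.2 would turn away a candidate whom 3.1 would let in. The monitor working from 9.3 has no definition of whether a waived subject is eligible.

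**Working it through.** No formula decides this point, and the plan gives no figure to reproduce. The check is a comparison of texts.

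**1. Scope of the waiver.** Section 3.1 lists two inclusion criteria (age 18-80, female). Section 3.2 lists eight exclusions. The waiver sentence covers both lists, 2 + 8 = 10 criteria, and exempts none.

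**2. Conditions on the waiver.** There are three: Investigator approval, given case by case; timing before enrolment; and documentation by the Investigator and the Sponsor. All three govern how a waiver is made. None limits which criterion may be waived. The Sponsor records but is not named as approving. Section 10.1 requires IRB approval of protocol modifications, but nothing says whether an individual waiver is one.

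**3. Comparison with the other sections.**

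| Section | What it requires | Against the waiver in 3.1 |
|---|---|---|
| 3.1, first sentence | All inclusion criteria met | Conflicts with the sentence that follows it |
| 4.2 | Consent only if the criteria are met | Conflicts; no waiver route |
| 10.2 | Those unable to consent are not eligible | Conflicts; no waiver route |
| 9.3 | Director verifies that only eligible subjects enter | Undefined for a waived subject |
| 9.4.4 | Deviations reported and logged | Silent on whether a waiver is a deviation |

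The numbered enrolment steps in 3.5 contain no waiver step either.

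**4. Is there a second bar for each safety or consent exclusion?**

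- *Capacity to consent:* yes, in 10.2. Section 9.3 also has the director verify that written consent came before participation. The problem is a conflict between sections, and 3.1 is not the only governing text.
- *Pregnancy:* no separate bar outside 3.2.
- *Implanted cardiac device or untreated arrhythmia:* no separate bar outside 3.2.

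For the last two, only the general condition in 4.2 stands against the waiver, and the documents do not say which prevails.

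**5. Weight of one subject, for context.** Section 3.3 gives a goal of 8, a minimum of 5 and a maximum of 12. One subject is 1/5 = 20%, 1/8 = 12.5% or 1/12 = 8.3% of the sample. This is the weight of any subject, waived or not. The documents give no waiver frequency and no effect of a waived subject on bladder-base displacement, so no bias can be calculated.

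**6. A constraint on reporting.** Section 10.3 promises group-level analysis in publication so that individuals are not identifiable. If the primary summary were a mean (the plan does not name one) and were published with and without one waived subject, her value could be recovered as x = n × mean(all) − (n − 1) × mean(without her). At n = 8 that is x = 8 × mean(all) − 7 × mean(without her). The fix has to allow for this.

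**The case against.** The best defence is that the sentence restrains waivers more than it invites them: it insists on prior, individual approval and on two-party documentation. A general rule with a documented exception is not in itself a contradiction, and a subject with an approved waiver could be regarded as eligible for the purposes of 9.3. This stands in part. The conditions are real, and it would be wrong to describe the discretion as uncontrolled. They do not, however, put any criterion out of reach, and they do not settle the conflicts with 4.2 and 10.2.

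A reader might be tempted by stronger readings, which the documents do not support:

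- *That 9.3 sets an enrolment rule which 3.1 breaks.* The item in 9.3 is on a monitoring checklist. What can be said is that the check is undefined for a waived subject.
- *That people without capacity could simply be enrolled.* Section 10.2 bars them separately.
- *That the person doing the ultrasound could choose who enters and so steer the result.* Approval lies with the Investigator, and the documents do not say that the Investigator performs the scans.
- *That the primary result would be biased.* The subject weights above do not show this. It is plausible that waiving the BMI or neuromuscular exclusion could affect contraction or its imaging, but the documents give no reason for those criteria and no data on the effect.

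It can also be said that removing every waiver goes further than the harm requires. That is fair, and the fix therefore includes a narrower minimum.

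**Conclusion.** The point holds as a matter of subject safety and internal consistency. All ten criteria are waivable as written, including three exclusions that concern safety or consent, and two of those three (pregnancy and cardiac device or arrhythmia) have no separate bar elsewhere. Section 3.1 conflicts with its own first sentence, with 4.2 and, on capacity, with 10.2. The status of a waived subject under 9.3 and 9.4.4 is not stated.

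This is more than missing detail, because following 3.1 exactly would permit stimulation of an excluded subject within the protocol. The change should be made, but the finding is not evidence that the results would be distorted. It assumes that the waiver sentence means what it says and that no separate document, such as the screening checklist kept outside the protocol, narrows it. Nothing in the documents indicates that any waiver has been granted.

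**What to change.** Delete the waiver sentence in 3.1. At minimum, state there that the safety and consent exclusions cannot be waived, and say who besides the Investigator must approve any other waiver and whether the IRB is informed. Then reconcile 3.1, 3.2, 4.2, 9.3 and 10.2 so that all use one definition of an eligible subject.

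State in 9.4.4 that anyone enrolled against a criterion is logged as a deviation, and report the number of such subjects. In the analysis plan that 9.2 and 9.4.3 promise, say how their influence on the primary summary will be examined consistently with 10.3. One way is to state in words whether the conclusion changes when they are left out, without publishing paired summaries from which one woman's value could be derived. Section 5b carries the protocol over to men with few changes, so the correction should apply there too.

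The cost is small: one deleted sentence, a few lines of alignment, and an occasional near-miss candidate to replace. In a one-sitting study open to women aged 18 to 80, replacement should not be difficult.

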#### **Initial Screening:**

- Age:18-80y
- Gender: female

### **3.2 Exclusion Criteria**

A subject meeting any of the exclusion criteria at baseline will be excluded if:

- Moderate-severe stress incontinence\*: As determined by self-reported >3 accidents in 24-hr period
- Currently pregnant, may be pregnant (Unsure pre and peri-menopausal women should take a pregnancy test.)
- Active urinary tract infection (UTI)
- Pelvic pain, Painful bladder syndrome, underlying neurologic/neuromuscular disorder that may impact ability to partake in the trial
- implanted cardiac device or untreated cardiac arrhythmia
- Obesity as defined by BMI  $\geq 30$  (height, weight recorded)
- Anyone with impaired decision making, drug or alcohol dependence, or potentially suicidal.
- Anyone who lacks the capacity to consent for themselves or who requires a legal representative to give informed consent

\* Stress urinary incontinence: as determined by an answer of "Yes" to a standard question (from King's Health Questionnaire): "Do you lose urine with physical activities such as coughing, sneezing, running?"

### **3.3 Number of Subjects**

The goal is 8 subjects, up to 12, 5 minimum. The rationale for the small number is this is a single-arm pilot study with no comparator arm.

### **3.4 Subject Compensation**

Subjects will be compensated \$50 for their time in the form of gift cards or cash.

### **3.5 Study Enrollment Procedures**

Subjects will be recruited through normal standard of care visits, office visits, and current subjects. A flyer will be posted in the waiting room.

1. The study director will go through the "Screening" checklist, which will include initial screening inclusion and exclusion criteria.
2. The Screening checklist will be kept in a Screening Log binder at the site and each screened potential subject will be recorded on the initial screening log chronologically.
3. If the subject is a candidate, the study administrator or physician will describe the study, walk the subject through the consent and obtain consent.
4. Day 1 of the study may be on the same day as initial screening if time allows, or up to 21 days later.
5. If subject is still a candidate, then the subject will be entered into the enrollment log and assigned the next subject/enrollment number. A copy of the initial screening will be put in the Case Report Sheet and the subject number recorded.

### **3.6 Early Termination**

Not Applicable - as this is a single-sitting acute study.

### **3.7 Adherence Assessment**

Not Applicable - as this is a single-sitting acute study.

### 3.8 Concomitant Medications

Not Applicable - as this is a single-sitting acute study.

### 3.9 Randomization/ Blinding

Not Applicable - as this is a single-arm acute study with no randomization.

## 4. PROTOCOL

### 4.1 Research Method

The research methods use standard and published methods of recording type and level of incontinence. Additionally, published methods of using transabdominal ultrasound for measuring base of bladder and pelvic floor contractions will be used. Measurements of distance moved will be used.

### 4.1 Initial Screening

Screening is based on above Screening Checklist/ Exclusion Criteria.

### 4.2 Informed Consent

If the subject meets the criteria and reviewed by the study director, then a single Informed Consent will be explained and obtained from the study director.

### 4.3 Pre-test

Subjects will be instructed to follow a standardized bladder-filling protocol, consisting of voiding, drinking 500 ml of water and waiting 45-60min (ideally 60 min before US pictures taken, but set up may start earlier).

### 4.4 Ultrasound

Subjects will place the electrode on their perineal area based on instructions, and a test should be completed to see if the subject feels a contraction while slowly incrementing the generator. If the subject is not getting good skin contact, hair may need to be trimmed or shaved. If the subject feels there is not much of a contraction, the electrode can be repositioned (usually one inch posteriorly).

Subjects should be placed in a comfortable supine position with hips and knees flexed to 60°, with lumbar spine positioned in neutral position. (Subjects may have underwear/clothes on over electrode.) Subjects should not see the US image.

With transabdominal ultrasound imaging (ex. GE Voluson E6 ultrasound with a 5-9D curved linear array GE RIC probe), the probe should be placed supra-pubically, on the lower abdomen, in the mid-sagittal plane. The transducer should be angled to obtain a clear image of the inferior-posterior aspect of the bladder. A marker should be placed at the bladder base on the junction of the hyper- and hypo-echoic areas in the region at rest. A marker should be placed, marking the maximal displacement of the bladder base from resting position:

- 1) while doing a PFM Kegel contraction (Instructions should be the same to all: to draw in and lift the PFM.)
- 2) with the generator on, slowly incrementing, counting the clicks and making note of when they first feel a contraction, until a maximum comfortable intensity level.
- 3) at the maximum comfortable intensity level *while* doing a PFM Kegel contraction combined.

4) (Optional) with a second generator (Waveform B) on at maximum comfortable intensity level

After the three images and max displacement recorded, the test should be repeated and potentially the intensity increased to a new maximum level (the skin may get numb after which intensity increased.) There should be a minimum of 7 ultrasound images (1 baseline, 2 with Kegels, 2 with generator, 2 with Kegels and generator.)

Any evidence of prolapse visualized using ultrasound should be recorded on Case Report Form.

While the generator is on the ultrasound probe can be manipulated to see if there is any evidence or indication which muscles are being contracted. We want to understand which muscles in terms of depth (pelvic diaphragm with levator ani, or perineal pouch with sphincter urethrovaginalis, or more shallow perineal membrane) which may also help determine if localized around urethra or entire pelvic floor, and if there is a difference between Kegels and electrical stimulation.

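### The stimulation endpoint is a maximum displacement from one static rest marker, and no resting generator-off period is scored by the same rule, so a small positive reading cannot be told from background movement.

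*Combined protocol and SAP*

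**What the plan says.** Section 1.1 gives the key endpoint as "Displacement of bladder base during contraction". Section 8.4.1 restates it as pelvic floor movement under stimulation and names no comparator or threshold. Section 4.1 (Research Method) says "Measurements of distance moved will be used" and relies on published transabdominal ultrasound methods.

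Section 4.4 gives the scoring rule. The bladder base is marked once at rest. Then, for each active condition: "A marker should be placed, marking the maximal displacement of the bladder base from resting position". The conditions are Kegel alone, generator on, generator plus Kegel, and an optional second waveform. In the generator condition the intensity is raised slowly "until a maximum comfortable intensity level". The set is then repeated, and the image count is "There should be a minimum of 7 ultrasound images (1 baseline, 2 with Kegels, 2 with generator, 2 with Kegels and generator". A later paragraph of 4.4 adds: "While the generator is on the ultrasound probe can be manipulated", to look for which muscles are active.

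Section 5.3.2 sets the generator to cycle 6 s on and 6 s off. No section asks for the off periods to be scored. Section 3.9 confirms a single arm. Section 3.3 gives the size: "The goal is 8 subjects, up to 12, 5 minimum". Section 2.2 gives the reason for the study: "a more objective proof that the pelvic floor is actually contracting was requested".

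**The concern.** Rest and stimulation are measured by different rules. Rest is one static marker. Stimulation is the largest excursion found while the image is watched over a ramp whose length is not fixed. If the image moves at all, through breathing or a shift of the probe, the largest excursion tends to lie above a single resting position even when no muscle has contracted.

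Nothing in the required images shows how large that effect is. The baseline image supplies a reference position only. Kegel alone falls under the same maximum rule without the generator, but it shows what the rule reads when the subject contracts on purpose.

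At stake is the claim the study was set up to support. If displacement under stimulation turns out to be small, the investigators will have no reading of their own to say whether it exceeds background. A later SAP (promised in 9.2 and 9.4.3) can choose an analysis, but it cannot supply off-phase readings that nobody was required to take.

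**Working it through.** **Plan's own figures.** The plan gives no displacement, measurement error, threshold, alpha or power to reproduce. Its only sample-size arithmetic is in 8.2: 8 × (1 − 0.20) = 6.4, against 5-6 completers stated. That is close and is not in dispute here.

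**Inputs from the documents.** Two passes per condition (4.4); one rest marker used for both (4.4); maximum rule (4.4); n = 5, 8 or 12 (3.3).

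**Assumed inputs.** Each marker placement has an error with SD s. All results are in units of s, because the documents give no millimetre value. The image moves with SD m, in frames with correlation r from 0 to 0.8. The operator searches K = 6 frames and marks the selected one. The true displacement is d.

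**Step 1. Signed reading, maximum over K frames.**
Mean reading = d + m × E(maximum of 6 standard normals). For independent frames that expectation is 1.267. Values at r = 0.8 are simulated.

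| Motion SD m | Mean at d = 0 | Mean at d = 2 s |
|---|---|---|
| 0 | 0 | 2.00 s |
| 0.5 s | 0.38 s (r = 0.8) to 0.63 s (r = 0) | 2.38 to 2.63 s |
| 1 s | 0.75 s (r = 0.8) to 1.27 s (r = 0) | 2.75 to 3.27 s |

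The shift is zero without motion. With motion it does not fade as d grows.

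**Step 2. Unsigned reading, no motion (a secondary case).** The difference of two markers has variance 2s², so the mean is that of a folded normal:
√2 s × √(2/π) × exp(−d²/4s²) + d × [1 − 2Φ(−d/(√2 s))].
- d = 0: 1.13 s
- d = 1 s: 0.88 + 0.52 = 1.40 s
- d = 2 s: 0.42 + 1.69 = 2.10 s (from unrounded terms)

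This shift fades as true movement grows.

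**Step 3. Matched on-minus-off difference.** On-phase and off-phase are scored by the same signed rule over equal lengths, from the same rest marker. The expected maximum of the motion appears in both and cancels. The simulated mean is 0 at d = 0 and 2.0 s at d = 2 s in every motion case of Step 1.

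**Step 4. Precision.** Variance of the two-pass mean with no motion:
- Displacement from rest: 1 (shared rest marker) + 1/2 (two on markers averaged) = 1.5 s².
- On-minus-off: (1 + 1)/2 = 1.0 s², because the rest marker cancels.

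With motion SD 1 s the simulated values are 2.7-2.9 s² and 1.4-1.8 s². The on-minus-off SD across all cases is therefore about 1.00 to 1.33 s. The 95% CI half-width is t(0.975, n−1)/√n × SD:

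| n | t/√n | Half-width |
|---|---|---|
| 5 | 2.776/√5 = 1.242 | 1.24 to 1.65 s |
| 8 | 2.365/√8 = 0.836 | 0.84 to 1.11 s |
| 12 | 2.201/√12 = 0.635 | 0.64 to 0.85 s |

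These cover marker and motion error only. Differences between subjects in true contraction would widen them.

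**The case against.** **The plan already limits noise.** It has a standard bladder-filling routine (4.3), a fixed supine posture, an image hidden from the subject and a repeat of each condition (4.4). This stands as mitigation. None of these measures shows how much the maximum rule reads with the muscle at rest and the generator off.

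**There is a generator-off condition.** A reader might infer that nothing is scored without the generator. That is not so: Kegel alone is. What is missing is a resting, no-contraction period.

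**Direction may be settled elsewhere.** A reader might infer that displacement is unsigned, and so positive by construction. The protocol states no sign convention, but the marking sentence cites published methods (refs 14 and 15) that may fix one, and direction might be recoverable from stored images. Step 2 is therefore a possible reading only, and direction is a secondary point.

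**No test against zero is planned.** A reader might infer that the study would declare success falsely at some high rate. The documents set no test, threshold or success criterion and leave the analysis to a later SAP, so no false-positive rate can be attributed to the plan.

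**Probe manipulation.** A reader might infer that the probe is moved while displacement is being marked. Section 4.4 does not say so. The passage follows the marking sequence and serves the question of which muscles move. The order is simply not stated.

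**Off-phases are not precluded.** Seven images is a minimum, and off periods should be visible during live imaging. That is right, but scoring them is not required.

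**It is a pilot.** This justifies a small sample and no comparator arm. It does not explain leaving out a within-subject reference that the duty cycle already provides.

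**Conclusion.** The concern holds in a limited form and should be fixed before imaging starts. The plan has no null reading for its maximum rule, so a small positive displacement under stimulation would not by itself show that stimulation contracts the pelvic floor.

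The size is unknown. The illustration runs from no bias (signed reading, still image) to 1.27 s (signed, independent frames, motion SD 1 s). It rests wholly on assumed values of s, m, K and r. It does not show that background movement is large relative to a real contraction. A large displacement, time-locked to the on-phase, would be persuasive under the plan as written, although the plan does not ask for that evidence.

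Confidence is medium: the gap is plain in the text, but its practical weight depends on measurement error that the documents do not report.

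**What to change.** In 4.4 and 8.4.1, for the stimulation-only condition in each of the two passes:

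1. Once the maximum comfortable intensity already defined in 4.4 is reached, and before any probe manipulation to identify muscles, hold the probe still.
2. Mark the maximal displacement in one on-phase and in the adjacent off-phase of equal length, by the same rule and from the same rest marker.
3. Record each value with a sign, lift positive and descent negative.
4. Report the within-subject on-minus-off difference, averaged over the two passes, with its 95% CI, alongside displacement from rest. Base the statement that stimulation moves the pelvic floor on that difference. Keep displacement from rest for the 8.4.2 comparison of stimulation, Kegels and both.

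**Cost.** One extra marker and a short clip per pass, in the same sitting with the same operator and machine, and two more entries on the case report form (a sign and an off-phase value). No extra subjects are needed.

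**Limits.** The difference understates contraction if the muscle does not fully relax within 6 s, which is why displacement from rest should stay beside it. It does not remove other movement locked to the on-phase, such as an abdominal response. Whoever places the off-phase marker may also know the generator state, since the plan describes no reader blinding.
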